Additionally 20 control women will be recruited for primary comparison of urinary microbiome data with IC/PBS cases. Inclusion for controls: : 1) Females, age 21 to 65 years (no racial/ethnic restrictions); 2) No history of or current bladder or pelvic pain; 3) Generally stable health 4) English speaking **Exclusion**: 1) Patients with pacemaker or other neurostimulator (gastric/spinal) 2) History or current symptomatic urethral stricture, cystitis caused by tuberculosis, radiation therapy or Cytoxan/cyclophosphamide therapy; 3) Prior augmentation cystoplasty or cystectomy; 4) Systemic autoimmune disorder (such as Crohn's Disease, Ulcerative Colitis, Lupus, Rheumatoid Arthritis, or Multiple Sclerosis); 5) Systemic neuromuscular disease known to affect the lower urinary tract; 6) History of urogenital cancer (with the exception of minor skin cancer); 7) Current or imminent planned pregnancy/recent delivery <6 months; 9) Current pelvic floor physical therapy; 10) Current use of opioid medications (short or long acting) for pain; 11) Abdominal or pelvic surgery within the last 6 months. 12) No symptoms or diagnosis of UTI within the past 3 months. These women after screening for eligibility will complete a basic demographics form for controls (see attached) and provide one voided clean catch urine specimen. They will not be required to undergo physical examination or vaginal swab or complete any other additional questionnaires. Women will be recruited from the LUC Health Sciences campus and will be provided a parking sticker for their participation.

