D. DESIGN OVERVIEW: This prospective randomized single blinded study will compare the effect of true acupuncture compared with sham/minimal acupuncture in women with IC/PBS (n=30). Symptomatic IC/PBS participants will not be asked to stop taking standing medications such as neurological agents in order to participate in the study. All current medications will be recorded and will measured using the Medication Quantification Scale (MQS III)^{23,24}. They will be asked to refrain from use of short-acting opioids/acetaminophen/non-steroid anti-inflammatory medications during study visits. IC/PBS participants will engage in 7 acupuncture sessions once weekly. Initial visit would assess participant's response to needle insertion. Standard classical/true acupuncture treatment will be administered during 6 following visits to treatment group (n=15) and sham/minimal acupuncture will be administered to control group. Menstrual cycle time points will be recorded for each visit. Clean catch voided urine samples and vaginal swab will be obtained prior to initiation of intervention, on completion of intervention and 12 weeks post onset of study visits.

E. RESEARCH STRATEGY:

Specific Aim 1: To determine the safety and tolerability of acupuncture in women with IC/PBS.

Hypothesis 1: Acupuncture treatment (true and sham) will be safe and tolerable in women with IC/PBS.

Specific Aim 2: To determine if acupuncture is effective in reducing pain in women with IC/PBS compared to sham treatment.

Hypothesis 2: True acupuncture treatment will be effective in the treatment of pain in women with IC/PBS compared with sham/minimal treatment.

Specific Aim 3: To determine the association between acupuncture responders and the urinary microbiome.

Hypothesis 2: Acupuncture responders will exhibit change in the urinary microbiome compared with nonresponders after acupuncture treatment.

STUDY DESIGN/METHODS:

Acupuncture Component:

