This is a randomized, controlled, single-blinded, pilot trial to study the feasibility, safety, and efficacy of acupuncture in IC/PBS women. Women will be recruited from the patient population of the Loyola University Medical Center who meet criteria for diagnosis of IC/PBS. This trial had 2 arms comparing the treatment of IC/PBS symptoms with acupuncture or sham/minimal acupuncture (placebo). Thirty (30) patients with IC/PBS will be enrolled as study participants into the study. Fifteen (15) will be allocated in the treatment classical acupuncture + medical management of IC and fifteen (15) will be allocated in the control sham/minimal acupuncture + standard medical treatments of IC. The acupuncturist will interview each patient and perform an exam. A standardized acupuncture treatment will be assigned, and both groups will receive 7 acupuncture treatments that follow a standardized protocol on classical acupuncture points, with or without mild electrical stimulation versus sham/minimal acupuncture. Acupuncture needles are single use, sterile and disposable. Standard acupuncture treatment protocol will include 4 gates plus GV 20 to reduce anxiety and help with relaxation and to assess acupuncture naïve patient's response to needles during their first acupuncture encounter. Subsequent visits would include administration of curious meridian Chong Mo paired with Yang Ming. 4 Hz low level electrical stimulation will be applied. Control group will receive sham/minimal acupuncture with low level electrical stimulation. The sham intervention (also described as minimal intervention) will use superficial needle insertion at body locations not recognized as true acupoints. Patients will be explained that various acupuncture treatment protocols will be tested including "minimal acupuncture", therefore, the control group will not be aware of receiving sham acupuncture. These described acupuncture treatments are well accepted treatment protocols for women with pelvic pain and bladder complaints.

Acupuncture or sham needle treatments will be performed once a week for 7 weeks. All subjects will be reassessed following the 7-week intervention phase and then 12 weeks from initiation of study. All subjects will be treated by single acupuncture practitioner ([name]) who is also a board certified urologist specializing in IC/PPS and is a current associate member of American Academy of Medical Acupuncture and board eligible for the American Board of Medical Acupuncture.

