Clinical Measurements:

The following clinical parameters will be assessed in all participants at baseline and repeated at follow-up 12 weeks after initiation of PFPT:

Demographics: age, self-reported race and ethnicity, vaginal parity, body mass index, menopausal and hormone replacement status, prior treatment for IC/PBS and other pelvic floor disorders, tobacco and alcohol use, prior medical and surgical history, medications including pain medications measured by the Medication quantification scale (MQS III)^{23,24}), allergy history, social history

Standardized physical exam: Abdominal exam with vaginal assessment of pelvic floor muscle function generalized muscle tenderness exam²⁵

Pain location, duration, intensity: Brief Pain Inventory – Short form (BPI-SF)²⁶, VAS pain scale²⁷, Short Form McGill Pain Questionnaire²⁸, Body Pain Diagram

Pain functional impact: Pain disability index²⁹; Patient Global Response Assessment (GRA)³⁰

Urinary/Pain Symptoms: Female Genitourinary Pain Index (FGuPI)³¹, Interstitial Cystitis Symptom Index and Problem Index (ICSI, ICPI)³²

Sexual Dysfunction: Female Sexual Function Index³³

Psychological impact/Coping style: Pain Catastrophizing Scale (PCS)³⁴, Beck Depression Inventory, second version (BDI-II)³⁵, Beck Anxiety Inventory (BAI)³⁶

Clean catch voided urine specimen: for urinalysis, culture and microbiome analysis

Vaginal Swab: to exclude vaginal bacteria from voided urine specimen.

Urinary Microbiome Approach:

In order to elucidate changes in the bladder's microbiota and to understand how the host's immune response may contribute to IC/PBS, we propose a multidisciplinary approach that blends molecular biology, immunology, genomics and clinical assessment. We will use *de novo* sequencing to determine the composition of the bacterial community present in the urine of women with IC/PBS undergoing acupuncture treatment. Urine will be collected at three time points via clean catch voided urine specimen and vaginal swab: at baseline, post intervention completion and 12 weeks after the onset of the intervention.

Preliminary Data: In April, 2012, we published data concluding that bacteria are present in the bladders of culture-negative women without symptoms of UTI¹⁶. More recently, we completed an analysis of 13 urine samples from individual women with either stress urinary incontinence (SUI) or urgency/frequency (U/F) or both.

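### The vaginal swab is taken from cases only, so using it for its stated purpose would process case and control urine differently in the case-control microbiome comparison

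*Combined protocol and SAP*

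**What the plan says.** **Controls.** Section C (Study Population) states that "20 control women will be recruited for primary comparison of urinary microbiome data with IC/PBS cases". Each control is to "provide one voided clean catch urine specimen". The next sentence waives the swab: "They will not be required to undergo physical examination or vaginal swab or complete any other additional questionnaires".

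**Cases.** The acupuncture methods under Section E plan for thirty: "patients with IC/PBS will be enrolled as study participants into the study". Section D (Design Overview) says "Clean catch voided urine samples and vaginal swab will be obtained prior to initiation of intervention", and again at the end of the intervention and at 12 weeks. The Urinary Microbiome Approach repeats this: "Urine will be collected at three time points via clean catch voided urine specimen and vaginal swab".

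**Purpose of the swab.** Clinical Measurements gives one purpose: "to exclude vaginal bacteria from voided urine specimen".

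**Laboratory and analysis.** The Sequencing Approach isolates DNA from urine, and the Bioinformatics Approach keeps reads above a quality threshold. Neither says what is done with the swab. Section F models uropathogen relative abundance on treatment group, time and their interaction. Group there means minimal versus electro-acupuncture, and time has three levels.

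**The concern.** A case-control comparison of urine flora requires both groups' specimens to be collected and processed alike. Here the means of separating vaginal from urinary bacteria exists for cases and not for controls. If it is applied, the case profile is a cleaned one and the control profile is not.

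This would be a systematic error. It could show a difference where there is none, or distort a real one, and recruiting more women would not help. This comparison is the only stated reason for enrolling the 20 controls. The Background also faults earlier IC/PBS microbiome work partly because its urine may have been contaminated, so the protocol itself regards contamination as a threat to validity.

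**Working it through.** The plan gives no figure to reproduce on this point. The check is a specimen count, a reading of the analysis text, and two illustrations with assumed inputs.

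**1. Specimens as planned, before dropout**

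| | Women | Urine specimens | Swabs |
|---|---|---|---|
| Cases, baseline | 30 | 30 | 30 |
| Cases, all time points | 30 | 30 × 3 = 90 | 90 |
| Controls | 20 | 20 × 1 = 20 | 0 |

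Swab availability coincides exactly with case status.

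**2. Does the analysis text settle the matter?** No. Controls belong to neither acupuncture arm and have one specimen, so they do not fit the Section F model. No other case-control analysis is given. The laboratory text neither applies nor rules out swab-based exclusion. Two readings remain:

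- The swab is used as Clinical Measurements says. Case urine is altered and control urine cannot be.
- The swab is not used. Both groups' urine is treated alike and this bias is zero.

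**3. Illustration A: exclusion of taxa.** Assume identical flora in both groups. Let s be the share of urine reads from taxa subject to exclusion, whatever their origin, and f the fraction of those reads removed from case urine. Shares are then rescaled to sum to one. For any retained taxon:

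case value / control value = 1 / (1 − s × f)

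| | s = 10% | s = 30% | s = 50% |
|---|---|---|---|
| f = 0 (swab not used) | 1.00 | 1.00 | 1.00 |
| f = 0.5 | 1/0.95 = 1.05 | 1/0.85 = 1.18 | 1/0.75 = 1.33 |
| f = 1 | 1/0.90 = 1.11 | 1/0.70 = 1.43 | 1/0.50 = 2.00 |

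**4. Illustration B: removal of carry-over.** Let b be a taxon's share in the bladder, v its share in the vagina, and c the vaginal carry-over in voided urine. The observed share is (1 − c) × b + c × v. If carry-over is fully removed in cases only, the spurious control-minus-case difference is c × (v − b). With assumed b = 0.40 and v = 0.80:

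- c = 0.10: 0.10 × 0.40 = 0.04
- c = 0.30: 0.30 × 0.40 = 0.12
- c = 0.50: 0.50 × 0.40 = 0.20

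The difference is zero when v = b. With 30 versus 20 women, the standard error is SD × √(1/30 + 1/20). For an assumed between-woman SD of 0.20 to 0.30, a two-sided 5% t test (48 df) would reject with probability 7–10%, 27–53% and 62–92% respectively, although the bladder communities are identical.

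The values of s, f, b, v, c and SD are all assumed. The two models show that an artefact is possible and how it grows. They do not estimate its size in this trial.

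**The case against.** The strongest objection is that the harm depends on a step the plan never describes. The sequencing and bioinformatics text covers urine only. Read literally, all urine passes through one pipeline. Table 1 (Schedule of Measures) has no swab row. The stated purpose is a short phrase in a list of measurements and could mean checking a specimen for contamination rather than subtracting taxa. The comparison is secondary, is in none of the three Specific Aims and has no analysis in Section F. The ratios above rest on assumptions and cannot establish severity.

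Much of this stands. What the text establishes is a conditional problem of unknown size and narrow scope. However, exclusion is the only purpose the plan gives for the swab, so expecting it to be carried out is a fair reading. Using the swab only as a contamination check would still be possible for cases alone. The missing table row does not override Section D and the microbiome section, which both plan the swab. Clinical Measurements refers to all participants, but it describes women with baseline and follow-up visits, and Section C exempts controls expressly.

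It is also fair to say that the absence of a case-control analysis is a separate omission, and that swabbing controls would be another way to equalise the groups. The first adds no weight here. The second is a real alternative, but it adds a procedure the plan chose to spare controls.

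**Conclusion.** The concern holds in its conditional form. If the swab is used as stated, case status is confounded with specimen processing in the comparison that justifies the controls. If it is not used, this bias does not arise. The documents do not say which applies, and they give no basis for the size or direction of any effect on a particular taxon. Confidence is medium for that reason.

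The reach is limited. The comparison is secondary to the BPI-SF worst pain objective, which is unaffected. The randomised comparison and Aim 3, "To determine the association between acupuncture responders and the urinary microbiome", use cases only, all with swabs planned, so the asymmetry does not enter, although swab handling is undefined there too. This should be corrected, but it does not threaten the trial's main result.

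**What to change.** In Section F, state that the case-control microbiome comparison is cross-sectional, name its outcome, and specify un-subtracted voided urine from both groups (baseline specimens for cases) processed through one identical pipeline. Restrict swab-based exclusion to within-case analyses and describe that step alongside the sequencing methods. Report any swab-filtered case-control result only as a labelled sensitivity analysis.

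This costs wording only. It needs no new specimens or visits, so it works even if controls have already been sampled. The price is that vaginal contamination, which the Background criticises in earlier work, stays in both groups. It may differ between clinic cases and campus controls, and the plan should state this as a limitation.

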C. STUDY POPULATION: Women presenting with IC/PBS at the Urogynecology/Urology clinics at Lovola University Medical Center will be approached for research participation. A certified research team member will explain the purpose and procedures of the study. Potential participants who meet inclusion criteria and agree to participate will indicate their consent by signing the informed consent document. Consistent with prevalent research regulations and policies, a signed copy of the research consent document will be given to the participant and the investigator will keep the original research consent document. Enrolled participants with IC/PBS must meet all the following eligibility criteria: **Inclusion**: 1) Females, age 21 to 65 years (no racial/ethnic restrictions); 2) Symptoms of urinary frequency, urgency and suprapubic/bladder pain for > 6 months; 3) Generally stable health 4) An average bladder pain score of at least >3/10. Exclusion: 1) Patients with pacemaker or other neurostimulator (gastric/spinal) 2) History or current symptomatic urethral stricture, cystitis caused by tuberculosis, radiation therapy or Cytoxan/cyclophosphamide therapy; 3) Prior augmentation cystoplasty or cystectomy; 4) Systemic autoimmune disorder (such as Crohn's Disease, Ulcerative Colitis, Lupus, Rheumatoid Arthritis, or Multiple Sclerosis); 5) Systemic neuromuscular disease known to affect the lower urinary tract; 6) History of urogenital cancer (with the exception of minor skin cancer); 7) Current or imminent planned pregnancy/recent delivery <6 months; 9) Current pelvic floor physical therapy; 10) Current use of opioid medications (short or long acting) for pain; 11) Abdominal or pelvic surgery within the last 6 months12) No symptoms or diagnosis of UTI within the past 3 months

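### The case-control microbiome comparison has no matching or adjustment for age or menopausal status, so a difference could reflect these rather than IC/PBS

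*Combined protocol and SAP*

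**What the plan says.** Section C (Study Population) gives the purpose of the control group: "Additionally 20 control women will be recruited for primary comparison of urinary microbiome data with IC/PBS cases". The two groups come from different sources. Cases are "Women presenting with IC/PBS at the Urogynecology/Urology clinics", whereas for controls "Women will be recruited from the LUC Health Sciences campus and will be provided a parking sticker for their participation". The first two control inclusion criteria read "Females, age 21 to 65 years (no racial/ethnic restrictions); 2) No history of or current bladder or pelvic pain"; cases have the same age limits, and the exclusion lists are nearly the same.

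Controls "complete a basic demographics form for controls (see attached) and provide one voided clean catch urine specimen". They are exempt from the examination, the vaginal swab and all other questionnaires.

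More is recorded for IC/PBS participants. Section D (Design Overview) says "Menstrual cycle time points will be recorded for each visit", in the paragraph describing their visits. The demographics list under Clinical Measurements in Section E includes "menopausal and hormone replacement status". These women give urine at three time points: before the intervention, at its completion and at 12 weeks.

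Section F contains one microbiome model. It regresses relative abundance of uropathogen on acupuncture group, time and their interaction. It includes neither the control women nor any age or hormonal covariate.

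**The concern.** The case-control contrast is not randomised. Balance on age and hormonal status has to come from recruitment or from analysis, and the plan specifies neither. A shared range of 21 to 65 years spans the menopausal transition, so two groups can both satisfy it and still differ widely in their postmenopausal share. By recording cycle timing, menopausal status and hormone replacement in the IC/PBS women, the protocol itself treats these variables as relevant.

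If the groups differ on them and the microbiome varies with them, an unadjusted difference would be credited to IC/PBS. The only stated reason for enrolling the 20 controls is this comparison, so its interpretability is what is at stake.

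A second gap adds to this. Cases give three specimens and controls one, and the plan does not say which case specimen is compared. Two of the three are taken after needling has begun, and the protocol hypothesises that acupuncture alters the urinary microbiome. Using those specimens would mix a possible treatment effect into the disease contrast.

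**Working it through.** **No figure to reproduce.** The documents give no effect size, SD, power or sample-size basis for cases versus controls. The sample-size statement in Section F concerns the randomised pain comparison only.

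**Where could confounding be controlled?**
- Recruitment: same age limits and similar exclusions, but no individual matching, frequency matching or quota.
- Data collection: one control form, contents not shown; the text does not mention hormonal status or cycle timing for controls.
- Analysis: Section F has no case-control model and no covariate for one.

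**Illustration 1: a binary microbiome feature**

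Inputs from the documents: 30 cases ("Thirty (30) patients with IC/PBS will be enrolled as study participants into the study"), 20 controls, two-sided 5% test.

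Assumptions not in the documents:
- The postmenopausal share differs between cases and controls by 20 to 50 percentage points, with zero as the reference.
- Prevalence of the feature (for example, dominance by Lactobacillus, which is not an endpoint named in Section F) differs by 20 to 50 points by menopausal status, equally in cases and controls.
- Overall prevalence is near 50%, and there is no true disease effect.

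Formulas: bias = (difference in share) × (difference in prevalence). SE = √(0.25/30 + 0.25/20) = √0.02083 = 0.144. False-positive rate = P(|Z + bias/SE| > 1.96).

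| Case | Bias | Bias/SE | False-positive rate |
|---|---|---|---|
| No imbalance | 0 | 0 | 5% |
| Low, 0.20 × 0.20 | 0.04 | 0.28 | about 6% |
| Midpoints, 0.35 × 0.35 | 0.12 | 0.85 | about 14% |
| High, 0.50 × 0.50 | 0.25 | 1.73 | about 41% |

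**Illustration 2: a continuous measure**

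This is a simulated unadjusted t-test, 30 versus 20, with no disease effect, within-stratum SD of 1 and 20,000 runs per setting. The postmenopausal shares and a hormonal effect of 0.5 to 1.5 SD are again assumptions.

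| Postmenopausal share, cases vs controls | Bias (SD) | False-positive rate |
|---|---|---|
| 30% vs 30% | 0 | about 5% |
| 40% vs 20% | 0.10 to 0.30 | 6.5% to 13% |
| 50% vs 20% | 0.15 to 0.45 | 8% to 24% |
| 60% vs 10% | 0.25 to 0.75 | 13% to 58% |

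For scale, the true difference detectable with 80% power is (1.960 + 0.842) × √(1/30 + 1/20) = 0.81 SD. The largest bias in the table, 0.75 SD, is close to that.

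Both illustrations agree: the distortion is negligible when imbalance is small, material at moderate values, and serious only when both the imbalance and the hormonal effect are large.

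**The case against.** The strongest reply has four parts.

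**The control form is not visible.** A reader might infer that cycle day and menopausal status are not recorded in controls. The documents do not support that: the form is an attachment and may capture age, menopausal status, hormone use or last menses. All that can be said is that the text does not provide for it. This stands. But even a complete form would leave the contrast without matching, adjustment or a stated analysis.

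**An age gap is not shown.** A reader might also infer that campus controls will be younger and more often premenopausal. The plan does not say whether they are students, staff or others, and gives no age distribution for either group. This stands too. The weakness is that nothing prevents or corrects an imbalance if one arises.

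**There is some restriction.** Common age limits and exclusions, including pregnancy, recent delivery, urogenital cancer and recent pelvic surgery, do make the groups more alike. That is partial control and deserves credit, but it leaves age and menopausal status free to differ within 21 to 65.

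**The comparison is peripheral.** Section C calls it primary, but no Specific Aim concerns cases versus controls, and Section F makes BPI-SF worst pain primary and everything else secondary. This is a small pilot. This stands and limits the weight of the point.

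On specimens, the plan does not say that post-treatment samples will be used. A pre-intervention sample is already collected, so that gap needs only a sentence in the analysis section.

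**Conclusion.** The point holds as a design weakness in a secondary comparison. As written, the plan leaves the case-control microbiome contrast open to confounding by age and hormonal status, because it specifies no matching, no adjustment and no analysis. Bias is possible, not demonstrated, and its size cannot be derived from the documents.

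Under the first illustration the false-positive rate is about 5% with no imbalance, about 14% at the midpoints and about 41% only with both inputs at their maximum. These figures depend on assumed imbalances, assumed hormonal effects and a binary feature that the plan does not name as an endpoint, so they show scale and do not forecast a result.

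A reader might take this as a threat to the trial's main finding. It is not: the acupuncture-versus-sham pain comparison is randomised and does not use the control women.

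**What to change.** 1. In Section C, frequency-match the 20 controls to the IC/PBS women on age band and menopausal status while recruiting, for example under 40, 40 to 50 and over 50.
2. State what the control form records, and make sure it captures age, menopausal status, hormone use and date of last menses.
3. In Section F, add the case-control comparison. Name its outcome, use only the pre-intervention case specimen, and adjust for age and/or menopausal status. With 50 women, one or two covariates are about the limit.
4. If controls are already enrolled, make the adjusted baseline comparison the main one. If the needed items were not collected, report the result with that limitation stated.

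The cost is a recruitment quota, at most a few added questions on an existing form, and one additional analysis. The main downside is slower filling of the older control slots. Adjustment alone is weaker than matching if few controls fall in the older bands, so the quota is worth setting while recruitment is still open.

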The primary objective is to compare the mean BPI-SF worst pain score at following acupuncture between groups. All other analyses are secondary outcomes. A separate linear mixed effects model will regress each pain score outcome on group (minimal versus electro-acupuncture), time (baseline, end of treatment, or end of follow-up), and a group by time interaction. Random intercepts will be included to account for within-patient correlation. Adjusted means and standard errors will be estimated, and main effects and the group by time interaction will be formally tested within the mixed model. A similar linear mixed effects model will regress relative abundance of uropathogen on group, time, and the group by time interaction. Based on the prior work of Crew KD et al.³⁷, a sample size of 30 participants (15 per arm) was calculated to yield 90% power to detect a reduction of 2.5 on the BPI-SF worst pain item at a 5% significance level, assuming a standard deviation of difference in score between treatment groups of 2.5 points. This includes a dropout rate of 10% A reduction of at least 2 points on the BPI-SF worst pain item is considered to be a clinically meaningful decrease based on the literature³⁸. All statistical analyses will be two-sided and performed using SAS 9.4 (SAS Institute, Cary, NC).

G. FUTURE DIRECTIONS: The impact and potential benefits of identifying new nonpharmacologic treatment in women with IC/PBS will be critical to reduce disease severity and improve quality of life across female IC/PBS and all CPP subtypes. These same methods will be employed for future clinical trials in IC/PBS and other CPP subtypes. In future studies, participants could be reassessed monthly for 6 months after post-intervention assessment (6 months after completing the treatment protocol), and subjects who relapse could receive one to two booster/maintenance acupuncture sessions with additional studies performed on the urinary microbiome.

H. TIMELINE:

Research Activity	Year 1 (2013 – 2014)			
	Qt 1	Qt 2	Qt 3	Qt 4
Recruitment and Evaluation of Participants	Х	Х	Х	
Data Collection	Х	Х	Х	
Data Analysis/Manuscript writing/editing			Х	Х

REFERENCES CITED:

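### The pain model treats baseline as an outcome visit and has no covariates, so the end-of-treatment comparison absorbs chance baseline imbalance and loses precision

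*Combined protocol and SAP*

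**What the plan says.** Section F (Data Analysis/Sample Size Estimation) states the aim as "The primary objective is to compare the mean BPI-SF worst pain score at following acupuncture between groups". Each pain score is regressed on group, "time (baseline, end of treatment, or end of follow-up), and a group by time interaction". On correlation, the plan says "Random intercepts will be included to account for within-patient correlation". On testing, it says "main effects and the group by time interaction will be formally tested within the mixed model".

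The same section promises that "Adjusted means and standard errors will be estimated", but neither it nor any other section names an adjustment variable. The design sections mention no stratification on pain.

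The baseline score will be available. The Clinical Measurements section begins "The following clinical parameters will be assessed in all participants at baseline" and lists the BPI-SF, and Table 1 schedules the questionnaires at baseline, after treatment and at 12 weeks.

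**The concern.** Randomisation gives the two arms the same expected baseline pain, but this model estimates a separate baseline mean for each arm and so does not use that fact. A random intercept accounts for correlation within a woman. It does not by itself correct the arm comparison for where the arms started.

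With 15 women per arm, chance differences in baseline pain can be large relative to an effect of 2 to 2.5 points. The raw end-of-treatment comparison carries part of that difference into the answer. The change comparison subtracts too much of it and adds noise when the correlation is modest. This is a separate matter from which contrast is primary: whichever is named, the planned model gives its less efficient version.

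**Working it through.** **Inputs from section F.** 15 per arm, a difference of 2.5 points, SD 2.5, two-sided 5%, 10% dropout said to be included.

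**Assumptions.** The baseline-to-post correlation ρ is not in the documents; 0.3 to 0.7 is used. The SD of 2.5 is taken to apply at each visit; the wording in section F does not settle this, so the other reading is given in step 6.

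**1. The plan's own figure.** For the inputs above, section F says "a sample size of 30 participants (15 per arm) was calculated to yield 90% power". The two-arm formula gives n = 2 × (1.960 + 1.282)² × 2.5²/2.5² = 21.01, so 22 per arm, or 22/0.9 = 24.4, so 25 with dropout. Power at 15 per arm is 78.2% (normal) or 75.3% (t). The stated 90% is not reproduced. That is a separate problem, but it means that there is no spare power.

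**2. What the model estimates.** A random-intercept model with group, time and their interaction was fitted to one complete simulated data set. The end-of-treatment arm difference was −2.913, identical to the raw difference in post-treatment means. The interaction contrast was −1.828, identical to the raw difference in change. Neither contains any regression on baseline.

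**3. Size of chance imbalance.** The SE of the baseline difference is 2.5 × √(2/15) = 0.913. P(|difference| ≥ 1) = 2 × [1 − Φ(1/0.913)] = 27%. With a baseline SD of 2.0 it is 17%.

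**4. Precision.** The variance of each arm contrast, as a multiple of the raw post-treatment contrast, is 1 (raw), 2(1 − ρ) (change) and 1 − ρ² (baseline-adjusted). Adjusted over change is therefore (1 + ρ)/2. SEs at 15 per arm:

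| ρ | Raw post | Change | Adjusted |
|---|---|---|---|
| 0.3 | 0.913 | 1.080 | 0.871 |
| 0.5 | 0.913 | 0.913 | 0.791 |
| 0.7 | 0.913 | 0.707 | 0.652 |

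At ρ = 0.5 the variance ratio is 0.75 against either contrast, worth 1/0.75 = 1.33 times the patients. Estimating the baseline slope costs a little: the simulated SD of the adjusted estimate is about 0.81, so the gain actually realised is nearer (0.913/0.81)² = 1.27.

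**5. Simulation of the planned model.** 20,000 trials per ρ, 15 per arm, true difference −2.5, complete data. Each cell gives power, then the shift in the estimate per point of baseline imbalance.

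| ρ | End of treatment | Interaction (change) | Group main effect | Baseline-adjusted |
|---|---|---|---|---|
| 0.3 | 77.0%, +0.30 | 62.9%, −0.70 | 67.8%, +0.53 | 77.6%, 0.01 |
| 0.5 | 76.8%, +0.50 | 76.5%, −0.50 | 57.9%, +0.67 | 84.7%, 0.00 |
| 0.7 | 76.0%, +0.70 | 93.5%, −0.30 | 50.5%, +0.80 | 95.2%, 0.00 |

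The group main effect averages in the pre-treatment visit, so it estimates about −1.67 (two thirds of −2.5).

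**6. Sensitivity (normal approximation).**
- After 10% dropout (13.5 per arm), power rises from 73.8% for the raw contrast to 77.7, 85.1 or 95.3% with adjustment (ρ = 0.3, 0.5, 0.7).
- If 2.5 is the SD of change, the change contrast has 78.2% power at 15 per arm and the adjusted contrast 92.5, 88.5 or 84.4%.

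**The case against.** The strongest reply is that nothing here is invalid. Baseline as a response with a group-by-time interaction is a standard longitudinal model, and its contrasts are unbiased over randomisations. That is correct: the fault is error conditional on the imbalance that happens to occur, plus lost precision. It is not systematic bias.

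Second, the interaction contrast does use baseline, as a change score. This is also true, but it replaces an estimated slope by a slope of 1. It over-corrects whenever that slope is below 1, and with equal SDs it is less precise than the plain post-treatment comparison when ρ is below 0.5.

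Third, the gain depends on an unknown ρ. Against the better of the two planned contrasts, it is 0.6, 7.9 and 1.7 percentage points of power at ρ = 0.3, 0.5 and 0.7 (step 5). This limits the claim, but the better contrast cannot be known in advance, and adjustment is at least as good in each case.

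Fourth, the eligibility floor on average bladder pain may narrow the baseline spread. With a baseline SD of 2.0 and a post-treatment SD of 2.5 (assumed), the adjusted-to-change variance ratio is 4.69/5.25 = 0.89 at ρ = 0.5 and 3.19/3.25 = 0.98 at ρ = 0.7, so the advantage over the change contrast shrinks. The advantage over the raw contrast, 1 − ρ², does not depend on the baseline SD.

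Fifth, under dropout the random intercept does draw on the baseline value of a woman with missing visits. That recovers some information about her missing scores. It does not correct for a baseline difference between the arms.

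Finally, section E calls this a pilot. Efficacy on worst pain is nevertheless the stated primary objective, with a power claim attached.

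**Conclusion.** The concern holds. As written, the model leaves the baseline means of the arms unconstrained and includes no covariate, so its adjusted means are adjusted for no baseline characteristic. Each of its tests moves with chance baseline imbalance, and with complete data none is as precise as the baseline-adjusted contrast.

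Under an SD of 2.5 at each visit and 15 per arm, the gain in power over the end-of-treatment contrast runs from negligible at ρ = 0.3 (77.0 to 77.6%) to large at ρ = 0.7 (76.0 to 95.2%). Over the change contrast it runs the other way, from 62.9 to 77.6% at ρ = 0.3 down to 93.5 to 95.2% at ρ = 0.7. The direction is secure, but the size rests on ρ and on how the stated SD is read. This change should be made. The planned analysis would not be invalid without it.

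**What to change.** In section F, for BPI-SF worst pain and each other pain score, model only the two post-treatment visits, with group, visit, group by visit, the baseline value of that score, and baseline by visit. Report the arm difference at end of treatment from this model as the primary estimate.

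A close alternative keeps baseline as a response but forces a common baseline mean: drop the group main effect and keep time and the group-by-post-visit terms. The two are not identical when visits are missing, and a random intercept alone imposes one common correlation between visits, so the plan should name one model.

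The sentence on adjusted means should state what they are adjusted for. The change should be fixed before any unblinded analysis so that it cannot look post hoc.

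The cost is one sentence in section F, a small change to the SAS model and two extra parameters (one baseline slope per post-treatment visit). No new data are needed. It does not replace a correction of the sample size: on the normal approximation, with 2.5 as the SD of the post-treatment score, adjustment reaches 90% power only if ρ is at least about 0.54 with 15 per arm, or 0.60 with 13.5.
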